10.4 Acupuncture Expectancy Scale

During the screening period (and prior to randomization), participants will be queried regarding their expectations regarding the effects of acupuncture using the validated Acupuncture Expectancy Scale.²⁴ In order to not bias results due to knowledge of randomization assignment, this measure will be assessed prior to randomization in all study participants.

11.0 SUBJECT DISCONTINUATION OF ACTIVE TREATMENT

Subjects may be removed from this study at any time at their discretion. Subjects may also be removed from this protocol if they develop any untoward side effects from the study procedures (acupuncture).

If a subject withdraws consent to participate in the study or aspects of the study, attempts should be made to obtain permission to record survival data up to the protocol-described end of the subject follow-up period. Documentation in the medical record should state that the subject is withdrawing from the study and what, if any, selected data the subject will permit the investigator to obtain.

If a subject withdraws consent and has received less than 1 cycle of chemotherapy with associated study-specified treatment (including any planned acupuncture sessions for that cycle), an additional patient will be recruited. Patients who receive less than 1 cycle of chemotherapy will not be followed.

An explanation for discontinuing treatment is recorded for each subject discontinuing treatment on the appropriate CRF/eCRF. The PI must be notified immediately if a subject discontinues treatment. All subjects, irrespective of treatment status, will continue to be followed for survival. Treatment in this study must be discontinued for any of the following reasons:

- at Investigator's discretion;
- at the subject's request;
- if the subject enrolls in a trial of another investigational agent which does not permit concurrent treatment;
- if the patient misses both acupuncture sessions from cycle 1 of chemotherapy;
- Grade 4 or life-threatening toxicity (See Section 13, Adverse Events) attributable to the study intervention;
- change in chemotherapy regimen which no longer includes oxaliplatin;
- pregnancy.

If a patient discontinues use of oxaliplatin, he/she may continue to receive acupuncture either weekly or as protocolized (twice weekly every other week) until the completion of 3 months duration of acupuncture treatment.

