9.7 Duration of Follow-Up

Patients will not be followed after the intervention and end-of-treatment questionnaires are complete, with the exception of collection of data during waitlist control acupuncture visits if these are pursued.

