9.9 End of Treatment (EOT) Visit Schedule and Procedures

The EOT visits for all subjects who discontinue from the study should ideally occur 14 days after day 1 of the prior cycle of chemotherapy (which would be 11 days from the last acupuncture treatment). The EOT visit is permitted in the range of 7-30 days after the last use of (Arm A) acupuncture treatment or (Arm B) cryotherapy use but must occur prior to beginning another treatment or receiving another dose of chemotherapy. Procedures to be performed during the EOT Visit include:

- Physical Exam
- Administration of the final QOL measures
- Vital Signs
- Performance Status
- AE Assessment
- Concomitant Medication

As per 6.7. patients who are on the waitlist control arm and choose to use their acupuncture coupons will have the optional EOT visit for uniform data collection, but will also have limited data collected at the time of each acupuncture session to note any toxicities or major symptoms at the time of those visit.

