10.2 Quality of Life Assessments

These will be administered at baseline, 6 weeks, and 12 weeks. If a patient is receiving chemotherapy on the day of the assessments, the assessments must be completed before the chemotherapy treatment is administered.

At each time point the EORTC QLQ CIPN-20 (see Appendix D) will be used to assess neuropathy and targeted questions from the NCI-PRO CTCAE (Appendix E) for the assessment of fatigue, nausea, and anxiety. The Brief Pain Inventory (Appendix F) will be used to assess pain. An oral symptoms questionnaire (Appendix G) will be used to assess oral dysesthesia.

On cycle 4 day 8 (± 2 days), a mid-cycle assessment will be done for the EORTC-QLQ CIPN-20, NCI-PRO CTCAE, and BPI. This may be administered by phone, on paper and returned at next clinic appointment, or electronically.

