16.5 Statistical Analysis

Severity of CIPN (EORTC-CIPN-20 score) at 3 months will be summarized for each treatment arm, and treatment comparisons made via linear regression model with adjustment for baseline severity level. Adherence to acupuncture treatment among patients in the intervention arm will be described as a proportion with 95% confidence interval. Reasons for treatment non-adherence and delivered dose intensity of chemotherapy will be noted. Incidences of CIPN (grade 2 or higher), pain, fatigue,

nausea, and anxiety will be compared between treatment arms using Chi-squared or Fisher's exact tests as appropriate. As this is a pilot study, we will not have adequate power to adjust for covariates such as age, gender, and existing comorbidities.

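### Section 11.0 follows stoppers for survival, which the trial does not use, while no text secures the 3-month CIPN-20 once a patient discontinues early

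*Combined protocol and SAP*

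**What the plan says.** On data after stopping, section 11.0 of the combined protocol and SAP says: "All subjects, irrespective of treatment status, will continue to be followed for survival". On withdrawal of consent it says that "attempts should be made to obtain permission to record survival data up to the protocol-described end of the subject follow-up period", and that the record should show "what, if any, selected data the subject will permit the investigator to obtain". The same section also says: "Patients who receive less than 1 cycle of chemotherapy will not be followed".

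Section 9.7 says: "Patients will not be followed after the intervention and end-of-treatment questionnaires are complete". Its only exception is data collected at waitlist acupuncture visits.

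Section 9.9 begins: "The EOT visits for all subjects who discontinue from the study should ideally occur 14 days after day 1" of the preceding chemotherapy cycle. It allows a window of 7 to 30 days after the last acupuncture (Arm A) or cryotherapy (Arm B), and the visit must precede any further treatment or chemotherapy dose. The final quality-of-life measures are given at this visit. Section 10.2 lists the CIPN-20 among them, and Appendix B marks the patient-reported outcomes (PROs) under End of Tx.

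Section 16.5 fixes the analysis: "Severity of CIPN (EORTC-CIPN-20 score) at 3 months will be summarized for each treatment arm", with a linear regression adjusted for baseline. Survival appears in none of the objectives (6.1), endpoints (6.3, 16.2) or analyses (16.5).

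**The concern.** The one outcome that 11.0 tells staff to pursue after treatment stops is one the trial will not analyse. Nothing says that the primary outcome is still collected at 3 months from a patient who has stopped. The last CIPN-20 then comes from the EOT visit, possibly after fewer oxaliplatin doses than the 3-month assessment assumes. The analyst must either treat the 3-month score as missing or let the early score stand in for it, and 16.5 does not say which.

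Either route can distort the primary comparison if stopping is related to neuropathy or differs by arm. Section 5.1 says that neuropathy causes early cessation of chemotherapy. The trial is unblinded, and some routes out of it exist in Arm A only.

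**Working it through.** **The plan's own figures.** Section 16.3 gives 50 complete patients, 0.7 SD, one-sided alpha 0.05 and 80% power. With 25 per arm, the normal approximation gives 79.7% and the noncentral t gives 78.7%. Enrolment is 50/0.9 = 55.6, so 56. Both figures reproduce.

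**When the EOT score falls.** Inputs are 14-day cycles with no delays, acupuncture on days 1 and 3 (9.2), an ideal EOT 14 days after day 1 of the last cycle, and an outer limit of 30 days after the last session (9.9). Weeks are counted from cycle 1 day 1, as (study day − 1)/7.

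| Last cycle | Ideal EOT | Week | Short of week 12 by | Arm A latest EOT | Week | Short by |
|---|---|---|---|---|---|---|
| 2 | day 15 + 14 = 29 | 28/7 = 4 | 8 | day 17 + 30 = 47 | 46/7 = 6.6 | 5.4 |
| 3 | day 29 + 14 = 43 | 42/7 = 6 | 6 | day 31 + 30 = 61 | 60/7 = 8.6 | 3.4 |
| 4 | day 43 + 14 = 57 | 56/7 = 8 | 4 | day 45 + 30 = 75 | 74/7 = 10.6 | 1.4 |

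A patient who completes six cycles has the EOT on day 71 + 14 = 85, and 84/7 = 12 weeks. In the calendar the EOT column therefore is the 12-week assessment. It holds that place only for patients who complete the course.

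**How timing can differ by arm.** Sections 9.8 and 11.0 let a patient who stops oxaliplatin continue acupuncture to 3 months. Suppose oxaliplatin stops after cycle 3.

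- Arm A: a patient who continues acupuncture on the protocol schedule has a last session on day 73 (cycle 6 day 3), and the ideal EOT stays at week 12.
- Arm B: cryotherapy is tied to the oxaliplatin infusion (9.3), so its last use is day 29. If an EOT is triggered, the window is day 36 to 59, or weeks 35/7 = 5.0 to 58/7 = 8.3, and it closes sooner if another chemotherapy dose comes first.

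The same event can thus give scores several weeks apart in the two arms. In addition, only Arm A can be removed for missing both cycle 1 acupuncture sessions (9.2, 11.0).

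**Illustrative bias if the 3-month scores are missing.** With an equal outcome gap in both arms, the shift in the arm difference is (difference in missing fraction) × (gap between missing and observed patients, in SD). Both inputs are assumptions:

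- low: 0.10 × 0.5 = 0.05 SD, which is 0.05/0.7 = 7% of the design effect;
- high: 0.20 × 1.5 = 0.30 SD, which is 0.30/0.7 = 43%.

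Twenty points of 28 patients is 5.6 patients, against a planned total loss of 56 − 50 = 6. Ten points is 2.8 patients.

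**Illustrative power** (noncentral t, equal loss in both arms). With all 56 scored it is 82.7%; with 50, 78.7%; with 44 (about 20% loss, assumed), 73.9%; with 40 (about 30% loss, assumed), 70.2%.

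**The case against.** The strongest reply is that stoppers are not left unmeasured. Section 9.9 and Appendix B give everyone who discontinues a final CIPN-20, and 10.2 schedules the questionnaire at 12 weeks with no exemption for patients off treatment. This stands. A reader might infer that early stoppers have no later CIPN-20 at all, and the documents do not support that. What remains is that the EOT score is early, that 9.7 closes follow-up after it, and that no sentence carries the 12-week assessment past discontinuation. Patients who withdraw consent fully, or who receive less than one cycle, may have no later score.

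Other parts of the reply also hold:

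- The withdrawal sentence limits survival data to the follow-up period the protocol describes, so it is compatible with 9.7, and other data may still be sought. Only the sentence on all subjects conflicts with 9.7, and with the less-than-one-cycle sentence in 11.0.
- The survival sentence does not itself bias the primary analysis. The harm comes from what is not collected.
- Section 5.1 concerns stopping chemotherapy, not leaving the study. Some patients who stop oxaliplatin can reach week 12 under 9.8. However, 11.0 also lists a change to a regimen without oxaliplatin as a reason for mandatory discontinuation, so the plan does not settle who counts as an early stopper.
- This is a pilot, and the planned 10% loss already absorbs a few missing scores. That covers lost precision, but not loss related to outcome or arm.

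**Conclusion.** The point holds in a limited form and should be acted on. The survival instruction serves no endpoint and conflicts with 9.7. For a stop after cycle 2, 3 or 4, the last CIPN-20 falls 4 to 8 weeks before the 3-month point on the ideal date. In Arm A it is still 1.4 to 5.4 weeks short at the outer limit of the window. These timings assume no chemotherapy delays.

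The bias cannot be derived from the documents. The 0.05 to 0.30 SD range rests wholly on assumed missingness and outcome gaps and applies only to missing scores. It does not measure the effect of using an early EOT score as a substitute. A reader might take 0.30 SD as an expected bias. The documents do not support that, because it would need almost all the planned loss to fall in one arm. The direction is also open, since either arm could lose more patients.

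**What to change.** - **11.0:** replace the sentence on following all subjects for survival. Collect the CIPN-20 and other PROs at the 12-week point, and at 6 weeks if not yet reached, from every randomised patient who still consents, whatever the treatment status. On withdrawal, ask permission for these questionnaires.
- **Timing and route:** for patients who have stopped, set the assessment at 12 weeks from cycle 1 day 1. Section 10.2 says of the cycle 4 day 8 assessment: "This may be administered by phone, on paper and returned at next clinic appointment, or electronically". That route now covers only that assessment, so extend it to these questionnaires. Patients still on treatment keep the chemotherapy-timed schedule (10.1, Appendix B footnote 6), so that nobody with delayed cycles is scored before finishing them.
- **9.7, 9.9 and the less-than-one-cycle sentence in 11.0:** align with the above.
- **16.5:** state that an early EOT score is an additional assessment and not the 3-month value, and say how 3-month scores that are still missing will be handled.
- **Reconcile** the passages that allow acupuncture to continue after oxaliplatin stops (9.8, 11.0) with the mandatory discontinuation in 11.0 when the regimen no longer includes oxaliplatin.

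The cost is protocol and consent wording, plus one or two remote questionnaires per early stopper. The unused survival follow-up is removed.

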9.3 Cryotherapy

As per Seattle Cancer Care Alliance protocol, patients will hold ice chips in the mouth from up to 30 min prior through the end of the oxaliplatin infusion. The use and duration of ice chip exposure will be documented. Additionally, the use of ice packs on hands and/or feet (which is allowed, but not part of current standard-of-care cryotherapy) will also be documented. Duration of each will be recorded as 0, 1-30, 31-60, 61-90, 91-120, or >120 minutes. Patients will be given the Cryotherapy Questionnaire (Appendix O) on the day of infusion or contacted by study staff within 5 days of completion of their chemotherapy infusion and patient self-recall will be used to determine the method and duration of their cryotherapy (Appendices O and P). The Questionnaire may also be sent via email to be complete in the study portal.

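### For patients who stop oxaliplatin early, the permitted window for the last CIPN-20 visit is counted from a different event in each arm, and nothing ties these patients to week 12

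*Combined protocol and SAP*

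**What the plan says.** All references are to the combined protocol and SAP.

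- **Intended time point.** Sections 10.2 and 10.3 schedule assessments at baseline, 6 weeks and 12 weeks. Section 16.5 compares the CIPN-20 score at 3 months, adjusted for baseline.
- **EOT timing.** Section 9.9 first gives a target common to both arms, two weeks after the first day of the preceding chemotherapy cycle. It then permits EOT "7-30 days after the last use of (Arm A) acupuncture treatment or (Arm B) cryotherapy use" and adds that the visit "must occur prior to beginning another treatment or receiving another dose of chemotherapy".
- **EOT content.** The 9.9 list includes "Administration of the final QOL measures". In Appendix B the last column for patient-reported outcomes is End of Tx. There is no separate week-12 column, and footnote 7 refers to 9.9 for timing. Section 9.7 says: "Patients will not be followed after the intervention and end-of-treatment questionnaires are complete", with an exception only for waitlist acupuncture visits.
- **Cryotherapy.** Under 9.3, ice chips are held "from up to 30 min prior through the end of the oxaliplatin infusion".
- **Stopping oxaliplatin.** Section 11.0 lists "change in chemotherapy regimen which no longer includes oxaliplatin" among the reasons for which study treatment must end. Its last paragraph, repeated in 9.8, reads: "If a patient discontinues use of oxaliplatin, he/she may continue to receive acupuncture either weekly or as protocolized", up to 3 months of acupuncture. For patients off treatment, 11.0 names one kind of follow-up: "All subjects, irrespective of treatment status, will continue to be followed for survival".

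**The concern.** Cryotherapy is tied to the oxaliplatin infusion, so when oxaliplatin stops, Arm B's EOT clock starts. Arm A's clock starts at the last acupuncture session, and only Arm A has a permission that can move that session later. A site that follows 9.9 and books EOT as the final CIPN-20 visit could measure an Arm B patient soon after the last oxaliplatin dose, and a comparable Arm A patient weeks later.

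The primary comparison is the CIPN-20 at 3 months. Section 5.1 says CIPN can require early cessation of treatment, so the patients affected can include those with the outcome under study. Section 16.5 does not say how an early EOT score enters the 3-month analysis. Leaving such patients out is not free either: 16.3 needs complete data from 50 of 56 patients, an allowance of 56 − 50 = 6.

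**Working it through.** **Inputs.** Biweekly cycles with acupuncture on days 1 and 3 of six cycles (9.2), a window of 7 to 30 days and the before-next-dose limit (9.9), and cryotherapy only with oxaliplatin (9.3). Cycle 1 day 1 is day 1. No delays are assumed, and acupuncture that continues follows the protocol schedule.

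**The plan's own target first.** Cycle 6 day 1 is day 1 + 14 × 5 = 71. The common target is 71 + 14 = day 85, which is 12 weeks from day 1. The last acupuncture session is on day 73, so the target falls 85 − 73 = 12 days later. Section 9.9 says 11, a one-day counting difference of no consequence here.

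**Six cycles on time.** Arm A: 73 + 7 to 73 + 30 = days 80–103. Arm B: 71 + 7 to 71 + 30 = days 78–101. The windows differ by 2 days and both contain day 85. If chemotherapy goes on to a cycle 7 dose on day 85, both windows close that day.

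**Early stop, acupuncture continued.** Let the last oxaliplatin dose be on day L = 1 + 14(k − 1) for cycle k.

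- Arm B opens on L + 7. It closes on L + 30 if chemotherapy ends, or on L + 14 if the rest of the regimen continues on schedule.
- Arm A opens on day 80 for every k.
- The gap in opening day is 80 − (L + 7) = 73 − L.

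| Last oxaliplatin cycle | L | Arm B window, chemotherapy ended | Gap in opening day | Latest B to earliest A, chemotherapy ended | Latest B to earliest A, backbone continues |
|---|---|---|---|---|---|
| 1 | 1 | 8–31 | 72 | 80 − 31 = 49 | 80 − 15 = 65 |
| 2 | 15 | 22–45 | 58 | 80 − 45 = 35 | 80 − 29 = 51 |
| 3 | 29 | 36–59 | 44 | 80 − 59 = 21 | 80 − 43 = 37 |
| 4 | 43 | 50–73 | 30 | 80 − 73 = 7 | 80 − 57 = 23 |
| 5 | 57 | 64–87 | 16 | overlap, days 80–87 | 80 − 71 = 9 |

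For a cycle 3 stop with chemotherapy ended, Arm B is measured 7–30 days after the last oxaliplatin dose. Arm A is measured 80 − 29 = 51 to 103 − 29 = 74 days after it.

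**Early stop, acupuncture also stopped.** Arm A opens on L + 2 + 7, always 2 days after Arm B (day 38 against day 36 for cycle 3). The arms then agree, but after an early stop both windows open well before week 12.

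**Does the common target settle it?** Take the cycle 3 stop with acupuncture continued.

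- If chemotherapy ends, the target is 29 + 14 = day 43. That is inside Arm B's window but before Arm A's opens on day 80.
- If the backbone runs through cycle 6, the target is day 85. That fits Arm A, but in Arm B it is 85 − 29 = 56 days after the last cryotherapy, outside the 7–30 days.

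In each case the target falls outside one arm's permitted window.

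**Can Arm B satisfy both 9.9 and week 12?** Day 85 lies inside Arm B's window only for a cycle 5 stop with no further chemotherapy (64–87).

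**The case against.** The case for leaving the text alone has several parts.

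- **The arm-specific window is secondary.** Section 9.9 leads with a target common to both arms. For on-time completers that target is week 12, which explains why the calendar has no separate week-12 column. This stands. A reader might infer that 9.9 times the final visit differently by arm for everyone, but for completers the difference is 2 days.
- **Twelve weeks is stated without conditions, and nowhere is an early EOT score said to serve as the 3-month score.** This also stands, and it makes the harm conditional. Section 9.9 concerns subjects who discontinue from the study, and an Arm B patient who drops oxaliplatin but stays on the backbone has not clearly done so. The survival sentence in 11.0 does not say questionnaires stop. Even so, no sentence keeps early stoppers on the 12-week schedule, while 9.9, 9.7 and Appendix B together point to EOT as the last measurement.
- **Section 11.0 need not contradict itself.** The listed reason can mean a switch of regimen, and the later paragraph can mean dropping one drug. That reading is plausible, so a flat contradiction is not shown. However, dropping oxaliplatin from FOLFOX fits both descriptions, and the text does not separate them.
- **The large gaps need two conditions:** optional continued acupuncture, and EOT serving as the final measure. Correct.
- **Gaps of up to 77 days.** A reader might infer these from the weekly option, with sessions starting on the next cycle's day 1, capped at 12 in total and ending on day 78. Sections 9.8 and 11.0 fix neither the start day nor the number of sessions. Weekly sessions counted from day 3 of the last oxaliplatin cycle end on day 73 and return the gaps in the table. The larger figures should not be relied on.

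**Conclusion.** The point holds for patients who stop oxaliplatin early. If Arm A continues acupuncture as protocolized and EOT supplies the final CIPN-20, the permitted windows open 72, 58, 44, 30 or 16 days apart for stops after cycles 1 to 5. They do not overlap for stops after cycles 1 to 4, whether or not other chemotherapy continues. These figures assume 14-day cycles without delay.

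A reader might go further and infer that the primary comparison is biased, or biased towards one arm. The documents do not support that. They give no rate of early stopping, no time course for the CIPN-20 after oxaliplatin stops, and no statement that an early score will be used as the 3-month score. The number affected and the size and direction of any bias cannot be derived.

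What can be said is that the intended 12-week time point is not secured for these patients, and that following 9.9 as written can measure them at different times by arm. The sample size is not in question.

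**What to change.** Make one wording amendment.

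1. **In 9.7, 9.9, 11.0 and Appendix B footnote 7**, state that stopping oxaliplatin, cryotherapy or acupuncture ends study treatment only, that the 6- and 12-week assessments are still collected in both arms unless consent is withdrawn, and that an early EOT visit does not replace the 12-week assessment.
2. **Replace the arm-specific anchor with one rule for both arms.**
   - Patients still on oxaliplatin: 14 days after cycle 6 day 1 and before the next chemotherapy dose, moving with delays as now.
   - Patients who stopped oxaliplatin early: day 85 from cycle 1 day 1, with one window common to both arms, completed before any chemotherapy given that day.
3. **In 11.0**, reword the listed reason as *switch to a different chemotherapy regimen that does not contain oxaliplatin*, and say that dropping oxaliplatin from the same backbone falls under 9.8. This alone is not enough, because the permission to continue acupuncture is what produces the gaps.

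A single calendar window of days 80–101 for everyone, the overlap of the two completer windows, looks simpler but should not be used for patients still receiving oxaliplatin. It would allow a CIPN-20 on day 90, for example, 5 days after a cycle 7 dose on day 85, which 9.9 now rules out for EOT. A patient delayed by more than 101 − 85 = 16 days would be measured less than 14 days after cycle 6 day 1, or before cycle 6.

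The cost is small. Some 12-week assessments will be collected after study treatment has stopped. The CIPN-20 can be done by phone, on paper or electronically, as 10.2 already allows at cycle 4 day 8. The Neuropen and tuning fork tests need a visit.
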